## 7. RATIONALE AND GENERAL CONSIDERATIONS

### 7.1. Chronic myeloid leukemia

Chronic myeloid leukemia (CML) is a malignant hematological disease which belongs to the group of myeloproliferative syndromes (or myeloproliferative neoplasia according to WHO classification 2008 [1]). This hematologic disease is a rare disease, with 600 to 700 new cases per year (the incidence in France is estimated at 1 or 2 cases per 100,000 persons, and increasing with age) [2], accounting for 15% to 20% of all cases of leukemia [3]. Mean age at time of diagnosis is 54 years and the disease affects 1.4 males vs. 1 female patient. The prevalence, on the order of 6000 to 7000 patients in France, is on the increase because of a frank decrease in mortality rate, at least during the first 6 years after the diagnosis [2].

CML results from a specific chromosomal anomaly which occurs in hematopoietic stem cells, although the principal cause of this anomaly is not yet understood. It is characterized by the presence of a chromosomal marker in hematopoietic cells, the Philadelphia chromosome (Ph1 chromosome), which can be detected in 95% of patients with CML [4]. The chimeric protein BCR-ABL (Breakpoint Cluster Region – Abelson), resulting from

translocation t(9; 22) at the origin of the Philadelphia chromosome positive (Ph+), has a high tyrosine kinase activity responsible for leukemic transformation by resulting in excessive and persistent production of white blood cells.

The disease, referred to as chronic, develops gradually and evolves slowly in three successive phases, becoming increasingly resistant to treatments with progression of disease: chronic phase (CP CML), accelerated phase (AP CML) and blast phase (blast crisis) (BP CML). The majority of patients are diagnosed during the chronic phase. Without treatment, patients in chronic phase CML will progress to the accelerated phase in 4 to 6 years. Patients diagnosed during the accelerated phase have a life expectancy estimated at less than 12 months in the absence of treatment. Following the blast phase, patients live on average 2 to 4 months if they are not treated [4].

## **7.2. Therapeutic management of CML**

Management of CML has appreciably improved over the last 20 years, in particular since introduction of the oral tyrosine kinase inhibitors BCR-ABL, more than a decade ago. Before the introduction of targeted therapies – tyrosine kinase inhibitors (TKI) – median survival of patients with CML was estimated at 6 years [5].

Based on results of the phase III study entitled “IRIS” (International Randomized Interferon versus STI571) published in 2003, imatinib (Glivec®, Novartis, 2001 [6]), the first TKI marketed for treatment of CML in 2001, quickly replaced interferon alpha (IFN $\alpha$ ) as the 1st line treatment of reference of CML, whether in chronic phase (CP), accelerated phase (AP) or blast phase (BP) with a progression-free survival rate to accelerated phase of 83% at 7 years, and an overall survival rate of 88% during the same period [7].

However, imatinib is commonly associated with a certain number of toxicities and resistance. After 8 years follow-up in the IRIS study, only 55% of patients randomized to the imatinib-treatment arm were still under treatment, with discontinuations related to a lack of efficacy (17%), a loss of complete cytogenetic response (15%) or intolerance to imatinib (7%) [8, 9].

Second generation TKIs such as dasatinib (Sprycel®, Bristol-Myers Squibb, 2006 [10]) and nilotinib (Tasigna®, Novartis, 2007 [11]) subsequently have been developed for 2nd line treatment of CML in patients intolerant or resistant to imatinib. Dasatinib obtained marketing authorization (MA) as 2nd line treatment for all phases of CML: chronic, accelerated and blast phase. Nilotinib obtained MA as 2nd line treatment for patients in chronic and accelerated phase of CML. These two therapies have recently obtained MA as 1st line treatment of chronic phase CML. In France, only nilotinib (chronic phase) and imatinib (all

phases) are reimbursed as 1st line treatment [12]. Like imatinib, resistance or intolerance exist to these treatments, which require changes to treatments [13, 14].

In spite of recent advances in treatment and management of patients who have CML, an important unmet medical need persists for many patients who are resistant or intolerant to one or more TKI. Approximately one third of CML patients treated with imatinib do not achieve an optimum response to treatment [15]. Among patients who are resistant or intolerant to imatinib and who require treatment with dasatinib or nilotinib, approximately half do not maintain a durable cytogenetic response. A clinical study evaluating 2nd line treatment with dasatinib (n=91) or nilotinib (n=25) in 119 patients with CP CML for whom treatment with imatinib has failed, showed that 52% of patients discontinued treatment following development of resistance or intolerance [16, 17].

Treatment with bosutinib (Bosulif®, Pfizer, 2013 [18]) offers an additional alternative for patients with CML (all phases) resistant or intolerant to one or more previous therapies with TKI, and in whom imatinib, nilotinib and dasatinib are not considered as appropriate treatments.

### 7.3. Bosutinib (Bosulif ®, Pfizer)

Bosutinib is a TKI indicated in treatment of adult patients with Philadelphia chromosome positive CML (Ph+ CML) in chronic phase (CP), in accelerated phase (AP) or in blast phase (BP), previously treated with one or more TKI and for whom imatinib, dasatinib and nilotinib are not considered as appropriate treatments. Bosutinib has demonstrated its activity against the majority of mutations in the BCR/ABL domain resistant to imatinib, to dasatinib or to nilotinib, except for the T315I mutation. The European Medicines Agency (EMA) has granted marketing authorization, valid in the entire European Union, for Bosulif® in this indication on 27 March 2013 in the category of an orphan medicinal product [19]. This approval is based on results of a single-arm, phase II, multicentre clinical trial conducted on 570 patients resistant or intolerant to a previous targeted therapy with TKI (Study 200). Efficacy data observed are listed below [Table 1] according to phase of disease and treatment lines [20, 21]:

In 2006, in 2009 and more recently in 2013, the European Leukemia Net (ELN) group developed a series of basic definitions and recommendations which guide the diagnosis, the treatment approach and the follow-up that is appropriate to adopt for patients depending on progression of the disease [10]. Monitoring of response to treatment, successively characterized by a hematological response, a cytogenetic response and then a molecular response should be performed regularly in order to set up appropriate management. Blood sample collection, as well as bone marrow samples collected at regular intervals make it possible to monitor the course of the white blood cell count, the number of cells that are carriers of the Philadelphia chromosome and the BCR-ABL load [Table 2]. Concomitantly,

regular consultations with a hematologist and a clinical examination that he/she performs enable to control the patient’s overall health condition.

**Table 2 – Diagnostic tests and monitoring of response to treatment (ELN 2013)**

Type of response	Diagnostic test	Type of sample	Monitoring period
HR	Blood cell count	Blood sample	At time of diagnosis, and then every 2 weeks up to obtainment of confirmed CHR, and then at least every 3 months or as needed.
CyR	FISH	Bone marrow blood	At time of diagnosis, at 3 months, at 6 months and at 12 months up to obtainment of a CCyR, and then every 12 months. The karyotype can be replaced with FISH (in blood) only with the CCyR is reached.
	Karyotype	Bone marrow	
MR	RT-PCR	Blood sample	At time of diagnosis, and then every 3 months up to obtainment of an MMR, and then every 3 to 6 months.

#### 7.4. Study rationale

The evolution of treatments and management of patients with CML have made it a treatable chronic disease associated with possible functional cure. In the same capacity as choice of 1st line treatment, the choice of the treatment sequence should take into account previous lines of therapy, comorbidities and individual preferences.

In light of the availability of several targeted therapies for treatment of CP, AP or BC Ph+/CML, each with their own specific safety of use and tolerability profiles and their own concomitant mechanisms of resistance, it is important to evaluate the efficacy, safety, cross intolerance and current modalities for use (dose adjustment, temporary discontinuations, permanent discontinuations of treatment) of these treatments under real life conditions of use in France.

Adherence of patients to their treatment is essential in order to maintain the response to treatment. For the purpose of optimizing adherence to treatment, it is also important to evaluate the strategies used in clinical practice in terms of therapeutic management and management of adverse events related to treatment.

This study will make it possible to obtain data on the real-life conditions of use of bosutinib in treatment of CP, AP or BP Ph+/- CML, in patients previously treated with one or more TKIs and for whom imatinib, dasatinib and nilotinib are not considered as appropriate treatments.

This non-interventional study is designed as a PASS (Post-Authorization Safety Study) and it is conducted voluntarily by Pfizer.

## **8. STUDY QUESTION AND OBJECTIVES**

This observational study, whose primary objective is to evaluate the safety and the rate of discontinuation of treatment because of intolerance, is going to make it possible to describe management of adverse events (dose adjustment, temporary discontinuation, permanent discontinuation of treatment) under real life conditions of use in France.

### **8.1. Primary objectives**

Under real life conditions of use:

- To determine the proportion of patients with CP, AP or BP Ph+/- CML presenting with AEs considered related to bosutinib by the participating doctor according to:
  - type of adverse event;
  - grade of event: 1, 2, 3, 4 or 3/4.
- To evaluate the proportion of patients who permanently discontinued bosutinib following an AE considered related to bosutinib by the participating doctor.

### **8.2. Secondary objectives**

Under real life conditions of use:

- To determine the safety profile of bosutinib: AEs that occurred during treatment with bosutinib, AEs which required changes to treatment with bosutinib, biological and hematological toxicities that occurred with bosutinib.
- To evaluate adherence of patients to treatment of bosutinib, with the aid of a self-questionnaire completed by patients (Morisky Questionnaire).
- To evaluate quality of life of patients treated with bosutinib, with a self-questionnaire completed by patients (FACT-leu version 4 - Questionnaire specific for leukemia)
- To describe the modalities of treatment with bosutinib under real life conditions of use (dose adjustment and reason for adjustment, dose intensity, relative dose

intensity; duration of treatment, temporary discontinuations/permanent discontinuations and reasons for such discontinuations).

- To evaluate the cumulative response rates: hematological (PHR/CHR), cytogenetic (CCyR / MCyR/ PCyR) and molecular response (MMR/CMR).
- To evaluate efficacy of treatment with bosutinib:
  - Progression-free survival at 1, 2 and 3 years of patients treated with bosutinib
  - Overall survival (OS) at 1, 2 and 3 years in patients treated with bosutinib
  - The percent transformation to AP/BC
- To describe the modalities of hematological, cytogenetic and molecular responses: median time to occurrence of response, median duration of response, type of response according to dose.
- To describe characteristics of patients treated with bosutinib (demographic characteristics; previous medical conditions, comorbidities; duration between time of diagnosis and initiation of treatment; previous treatments and better response under these treatments; duration of previous treatments, reasons for discontinuation of previous treatments; the last hematological, cytogenetic or molecular responses known).
- To evaluate cross intolerance between bosutinib and tyrosine kinase inhibitors prescribed previously.

## **9. STUDY METHODS**

This non-interventional study protocol has been submitted to an internal validation committee in conformity with Pfizer standard procedures.

### **9.1. Study design**

This is a national, observational, descriptive, prospective, multicentre study conducted in metropolitan France in adult patients treated for accelerated or blast phase Philadelphia chromosome positive chronic myeloid leukemia, previously treated with one or more TKIs and for whom imatinib, nilotinib and dasatinib are not considered as appropriate treatments. The study will be conducted in all centres involved in management of CML, i.e. about twenty (20) in expected centres.

[figure not shown]
The study will be offered to the totality of patients who satisfy criteria for inclusion and for non-inclusion up to the end of the inclusion period defined as 4 years. About one hundred

(100) patients included are expected in the study. Therapeutic management of a patient will not be changed by participation in the study and will depend on decisions taken by doctors in agreement with current international recommendations (European Leukemia Net, ELN network [13]) (see paragraph 7.3).

Patients will be followed prospectively over a 3-year period starting with their inclusion in the study. The inclusion visit will be performed at time of inclusion of the patient in the study, after which the patient has been informed and has accepted to participate by signing the consent form. Follow-up visits will be performed after usual consultation, estimated at about every 3 months. No visit or additional examination will be requested by the protocol: modalities for follow-up and treatment will be left up to the entire judgement of the participating doctor. Data will be recorded during the 3 years of the patient's participation, except in case of withdrawal of consent, death of a patient or termination of the study before its planned end.

Total duration of the study is estimated at 7 years with an inclusion period of 4 years and a follow-up period of 3 years (see Figure 1). Throughout the study, at least one monitoring visit per year will be performed.

**Figure 1 – Overall study flowchart**

## 9.2. Context

This study, conducted in metropolitan France, will include patients who satisfy eligibility criteria defined below.

Eligible patients but not included in the study will be reported in a registry of non-inclusion with a minimum collection of information (see [9.4.1.7 Registry of non-inclusion](#)).

### 9.2.1. Criteria for inclusion

Patients must satisfy all of the following criteria for inclusion in order to be eligible.

- Male or female patient 18 years of age or older;
- Patient with BCR-ABL Philadelphia chromosome positive or negative CML, in chronic, accelerated or blast phase;
- Patient resistant or intolerant to previous therapy with TKI for CP, AP or CB CML other than bosutinib;
- Patient initiating treatment with bosutinib for treatment of CP, AP or BP phase Ph+ / - CML at the end of the inclusion visit or during the one month prior to it;
- Patient who has been informed that a method of contraception must be used if a risk of pregnancy exists.
- Patients who have been informed about the study and who signed the informed consent form.

### 9.2.2. Criteria for non-inclusion

Patients who satisfy one of the following criteria will not be included in the study:

- Patient with chronic, accelerated or blast phase BCR-ABL Philadelphia chromosome negative CML;
- Patient recently diagnosed with CML and who has not received previous treatment with a TKI;
- Patient currently treated with a treatment other than bosutinib;
- Patient of childbearing potential not using a method of contraception;
- Patient treated in the setting of an interventional study for another disease (outside of follow-up period);
- Patient who refuses computer processing of his/her medical data.

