#### 4. SYNOPSIS

Title	BOSEVAL: An observational study - Evaluation of efficacy and safety of Bosulif® under real life conditions of use
Identifier of protocol version	Version 2.0
Date	15-FEB-2019
RATIONALE:	In spite of recent advances in treatment and management of patients with chronic myeloid leukemia (CML), an important unmet medical need persists for many patients who are resistant or intolerant to one or more tyrosine kinase inhibitors (TKI). Treatment with bosutinib offers an additional alternative for patients with CML resistant or intolerant to one or more previous therapies with TKI. In light of the availability of several targeted therapies for treatment of CML, each of which has a specific safety and tolerability profile, it is important to evaluate the efficacy, safety and modalities for use of these treatments under real-life conditions in France. This non-interventional study will make it possible to obtain data under real-life conditions of use of bosutinib in treatment of CML (all phases combined) in patients previously treated with one or more TKI and for whom imatinib, dasatinib or nilotinib are not considered as appropriate treatments.
OBJECTIVES:	
Primary objectives:
 
 
- To determine the percentage of patients with chronic phase (CP) Ph+/- CML or blast phase CML presenting with AE considered related to bosutinib by the participating doctor.
 
- To evaluate the percentage of patients who permanently discontinued bosutinib after an AE considered related to bosutinib by the participating doctor.
 
 
Secondary objectives:

	
 
- To determine the safety profile of bosutinib.
 
- To evaluate adherence of patients to treatment with bosutinib.
 
- To evaluate quality of life of patients treated with bosutinib.
 
- To describe modalities of treatment with bosutinib under real life conditions of use.
 
- To evaluate the efficacy of treatment with bosutinib.
 
- To describe the hematological, cytogenetic and molecular responses.
 
- To describe the characteristics of patients treated with bosutinib.
 
- To evaluate cross intolerance between bosutinib and previously prescribed tyrosine kinase inhibitors.
 

Study Design	
Non-interventional observational multicentric prospective study not affecting the patient's medical care.

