POPULATION CONCERNED:	
Criteria for inclusion:
 
 
• Male or female patient 18 years of age or older;
 
• Patient with Philadelphia chromosome positive or negative CML, or BCR-ABL positive, chronic, accelerated or blast phase;
 
• Patient resistant or intolerant to previous therapy with a TKI for CP, AP or BP CML other than bosutinib;
 
• Patient initiating bosutinib for treatment of CP, AP or BP Ph+/- CML, at the end of the inclusion visit or during the month preceding it;
 
• Patient who has been informed that a method of contraception must be used if a risk of pregnancy exists;
 
• Patient who has been informed about the study and who signed his or her consent form.
 
 
Criteria for non-inclusion:
 
 
• Patient with Philadelphia chromosome
 

	
negative CML, BCR-ABL negative chronic, accelerated or blast phase CML.
 
 
• Patient recently diagnosed with CML and who has not received previous treatment with TKI;
 
• Patient currently treated with a treatment other than bosutinib
 
• Patient of childbearing potential not using a method of contraception;
 
• Patient treated in the setting of an interventional study for another disease (outside of follow-up period);
 
• Patient who refuses computer processing of his/her medical data.
 

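### Section 9.2.2 of the protocol, read literally, excludes the Ph-negative patients that section 9.2.1 includes, and the non-inclusion registry would not show the loss

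*Protocol*

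**What the plan says.** Protocol section 9.2.1 requires every inclusion criterion to be met. One is "Patient with BCR-ABL Philadelphia chromosome positive or negative CML, in chronic, accelerated or blast phase". Another is "Patient initiating treatment with bosutinib for treatment of CP, AP or BP phase Ph+ / - CML". Both put Ph-negative disease inside the study.

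Section 9.2.2 opens with the rule "Patients who satisfy one of the following criteria will not be included in the study". The first criterion below it is "Patient with chronic, accelerated or blast phase BCR-ABL Philadelphia chromosome negative CML".

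The synopsis (section 4) also admits Ph-positive or Ph-negative disease, or BCR-ABL-positive disease. Its exclusion carries a second negative that 9.2.2 lacks: after the words Philadelphia chromosome it continues "negative CML, BCR-ABL negative chronic, accelerated or blast phase CML".

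The primary objective in section 8.1 reads "To determine the proportion of patients with CP, AP or BP Ph+/- CML presenting with AEs considered related to bosutinib". The synopsis gives the same objective as "To determine the percentage of patients with chronic phase (CP) Ph+/- CML or blast phase CML presenting with AE considered related to bosutinib", without accelerated phase. The opening sentence of section 9.1 describes "adult patients treated for accelerated or blast phase Philadelphia chromosome positive chronic myeloid leukemia", without chronic phase and without Ph-negative disease.

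**The concern.** Eligibility criteria are operative text. Section 9.3 makes compliance with them a recorded variable, and section 9.8.2 has monitors check compliance with the protocol. When an inclusion and an exclusion criterion collide, the exclusion prevails, because one is enough to bar a patient. A doctor who reads 9.2.2 as written should therefore turn away each Ph-negative patient that 9.2.1 invites in. A doctor who works from the synopsis may enrol a patient who is Ph-negative but BCR-ABL positive.

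The protocol's defence against selection is consecutive inclusion (sections 9.5 and 9.9.2) backed by the registry of non-inclusion. Section 9.4.1.7 and Annex 3.7 restrict that registry to patients who pass the eligibility criteria but do not enter. A patient refused under 9.2.2 has failed a criterion and is not logged. The comparison of included with non-included patients therefore cannot reveal this selection. At stake is whether the primary percentages describe the Ph+/- population that 8.1 names.

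**Working it through.** **Side-by-side reading.** Take a patient with Ph-negative, BCR-ABL-positive CML who meets every other criterion.

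| Text | Outcome for this patient |
|---|---|
| 9.2.1, disease criterion | included |
| 9.2.1, treatment-start criterion (Ph+/-) | included |
| 9.2.2, first criterion, literal | excluded |
| Synopsis, inclusion criterion | included |
| Synopsis, exclusion, read as negative for both | not excluded |
| 8.1, primary objective (Ph+/-) | covered |
| Annex 3.7 registry, if refused under 9.2.2 | not recorded |

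The phrase pairing BCR-ABL with Philadelphia chromosome is built the same way in 9.2.1 and 9.2.2, with no separate sign on BCR-ABL. Nothing within section 9.2 tells the reader that the exclusion is narrower than the Ph-negative group just included.

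**The plan's own precision figure.** Section 9.5 states a half-width of at most 10 points for a percentage, from about 100 patients, by the Wald method without continuity correction at a 50% rate.

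- Formula: half-width = 1.96 × √(0.5 × 0.5 / n).
- n = 100: 1.96 × √(0.25/100) = 9.80 points. The stated figure reproduces.
- Smallest n for 10 points or less: 1.96² × 0.25 / 0.10² = 96.04, so 97 patients.

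**Possible number affected.** Section 7.1 says the Philadelphia chromosome is detectable in 95% of patients with CML. Assume that this share holds among the pretreated patients entering this study.

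- Expected Ph-negative patients: 100 × (1 − 0.95) = 5.
- Central 95% range of a binomial with n = 100 and p = 0.05: 1 to 10.
- Probability of at least one: 1 − 0.95^100 = 0.994.

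Five is an upper figure for the expected number in dispute. Ph-negative patients who are also BCR-ABL negative would be excluded under the synopsis reading too, and the protocol does not give that split.

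**Effect on precision.** If 5 patients were lost and not replaced, n = 95 gives 1.96 × √(0.25/95) = 10.05 points.

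**Effect on the estimate.** Leaving out a 5% subgroup shifts the overall percentage by 0.05 × the difference in rate between that subgroup and the rest. For an assumed difference of 20 to 50 points, the shift is 1.0 to 2.5 points.

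**The case against.** The best defence is that 9.2.2 is a garbled form of the synopsis criterion. If its single negative is taken to govern both BCR-ABL and the Philadelphia chromosome, only patients negative for both are excluded and the conflict disappears. The synopsis supports that reading, sites are monitored at least once a year, and the effect on a descriptive percentage is small. All of this is fair, and it limits the size of the point. It does not remove it: the reading has to be brought in from the synopsis, and the full criteria in section 9.2 do not state it.

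It can also be said that section 7.3 gives the indication as Ph-positive CML, so the exclusion might be the intended rule. But 8.1, 9.2.1 and 9.7.1 all say Ph+/-, and section 5 records that the amendment was written to bring Ph-negative patients into the analysis. The intent leans one way. The sponsor still has to confirm it.

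Three stronger readings are tempting and are not supported.

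- A reader might infer that the 9.1 sentence removes chronic-phase patients, or that the synopsis objective removes accelerated-phase patients, and might size the loss from the phase mix in the study 200 table. Neither text decides eligibility. Section 9.2 assigns that to the criteria below it, section 9.7.2 describes the primary percentage overall, and the synopsis criteria, 8.1, 9.2.1 and 9.7.1 all cover the three phases. No patient is lost.
- A reader might infer that cytogenetic response and the Ph-based part of the progression definition have been left without a denominator for Ph-negative patients. Section 9.7.3 leaves the detail of the secondary analyses to the SAP, which is not at hand, so this is not a finding.
- A reader might infer that the roughly 20 centres are already applying different rules. The protocol permits this but gives no evidence that it has happened.

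**Conclusion.** The contradiction between 9.2.1 and 9.2.2 is real, stands in the current text and concerns an operative rule, so it must be corrected. It rests on the wording alone and on no numerical assumption.

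Its numerical weight is modest: at most about 5 of 100 patients, with a binomial range of 1 to 10, if the 95% share for CML in general carries over to this cohort. The half-width would then exceed the stated 10 points only marginally. The reason to act is that the study's own check on selection cannot detect a refusal made under 9.2.2. The discrepancies in 9.1 and the synopsis objective are drafting slips that need alignment and have no effect on the denominator.

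**What to change.** Reconcile 9.2.1, 9.2.2 and the synopsis into one eligibility rule and state it identically in all three places. The synopsis exclusion, together with the Ph+/- scope of 8.1 and 9.2.1, points to excluding only CML that is both Ph negative and BCR-ABL negative; the sponsor should confirm this.

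Send centres a short clarification. In the same letter, ask whether any Ph-negative, BCR-ABL-positive patient was refused under 9.2.2, and report the number with the registry comparison.

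As editorial alignment, correct the opening sentence of 9.1 and the synopsis primary objective so that both cover CP, AP or BP Ph+/- CML.

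The cost is a few wording changes and one letter to about 20 centres. The sample size and the analysis do not change.

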#### **9.4.1.7. Registry of non-inclusion:**

Patients eligible but not included must be recorded in a non-inclusion registry (*see ANNEX 3.7: Registry of non-inclusion*), with a minimum of parameters collected:

- Demographic characteristics (year of birth, gender),
- Reason for non-inclusion.

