### **9.7.2. Analysis of the primary objectives**

The following parameters will be evaluated in order to respond to the primary objectives:

- The percent of patients presenting with adverse events considered related to bosutinib by the participating doctor will be described overall (all grades of seriousness combined, all types of events combined), depending on grade: 1, 2, 3 and 4 and grades 3/4, and by type of event.
- The percent of patients who permanently discontinued treatment with bosutinib following an AE considered related to bosutinib by the participating doctor will be described overall.

Analysis of the primary objectives will be detailed in the statistical analysis plan.

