### **9.9.2. Selection bias of patients**

The representativeness of the sample of the study compared to the target population is basic in order to be able to extrapolate results of the study to the target population. The representativeness of the sample depends on internal validity (precision of estimates and selection criteria of study population – the patients) and the outside validity (plan and fluctuations of sampling).

The representativeness of patients included is a potential selection bias in observational studies. Conscious selection or not of patients in the study by participating doctors is inevitable. Participating doctors will be asked to include sequentially and exhaustively all patients who satisfy eligibility criteria for the study up until the end of the inclusion period in order to limit this bias. Parameters on representativeness of patients included will be controlled by the set-up of a registry of non-inclusion up until the end of the inclusion period.

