### **INSTRUCTIONS FOR COMPLETING THE REGISTRY OF NON-INCLUSION**

the registry of non-inclusion is to be completed during the inclusion period of the BosEVAL study for all adult patients who satisfy criteria for inclusion and for non-inclusion but who have not wanted to participate in the study.

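### Patients who start bosutinib, stop it for a related AE and switch before the inclusion visit are neither included nor logged, so the pooled discontinuation percentage can understate early toxicity stops

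*Protocol*

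**What the plan says.** **Entry window.** Protocol 9.2.1, like the synopsis, admits patients who begin bosutinib "at the end of the inclusion visit or during the one month prior to it". Section 11.3 has a separate start of AE reporting (the consent date) for patients already exposed, so the protocol expects such entrants.

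**Bar to entry.** Section 9.2.2 and the synopsis exclude a "Patient currently treated with a treatment other than bosutinib". No exception is made for a patient who began bosutinib inside the window and has since changed treatment.

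**Registry.** Section 9.4.1.7 states: "Patients eligible but not included must be recorded in a non-inclusion registry". Section 9.2 says the same. The instructions in Annex 3.7 narrow this to "all adult patients who satisfy criteria for inclusion and for non-inclusion but who have not wanted to participate in the study".

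**Endpoint.** For the second primary objective, 9.7.2 states: "The percent of patients who permanently discontinued treatment with bosutinib following an AE considered related to bosutinib by the participating doctor will be described overall". Patients included at first dose and patients included later are not distinguished.

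**Safeguards.** Section 9.5 relies on consecutive inclusion of eligible patients for representativeness, and 9.9.2 adds: "Parameters on representativeness of patients included will be controlled by the set-up of a registry of non-inclusion". The limitations in 9.9 do not mention patients lost between first dose and the inclusion visit.

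**The concern.** Where inclusion follows the first dose, entry depends partly on the outcome being measured. A related AE that leads quickly to a permanent stop and a new treatment removes the patient from both the numerator and the denominator of the second primary endpoint. This is left truncation, and the loss of these patients lowers the reported percentage. The confidence interval does not reflect it.

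The cross-intolerance measure in 9.7.3 is also built on permanent discontinuation for an AE and inherits the problem. The registry cannot help, because it describes only patients who met the criteria. A later analysis plan can model delayed entry, but it cannot recover patients whom the protocol never records.

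The point concerns who can enter the cohort for the discontinuation endpoint. It does not concern survival time, or how AEs and doses are recorded in patients who do enter.

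**Working it through.** **1. The plan's own precision figure.** Section 9.5 gives a half-width of at most 10 points for about 100 patients, by the Wald method at 50%: 1.96 × √(0.5 × 0.5 / 100) = 9.8 points. This reproduces. At 20% the half-width is 1.96 × √(0.2 × 0.8 / 100) = 7.8 points.

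**2. Who is lost.** All of the following must hold before the inclusion visit and within one month of first dose: bosutinib started, a related AE occurred, bosutinib was stopped permanently, and another treatment was begun. If the last condition fails, 9.2.2 does not bar the patient. If the patient is included at initiation, nothing is lost.

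**3. Inputs.**
- D = 0.20, the true share stopping for toxicity. Section 7.3 gives approximately 20% in study 200, but for any AE, so it is only an anchor for a related-AE endpoint.
- f = 0.25 to 0.40, the fraction of those stops falling in month 1 (assumed).
- L = 0.5 month, the mean lag from first dose to inclusion among late entrants (assumed).
- s = 0.5, the share of the cohort included after starting (assumed).
- w = 0.5 to 1, the fraction of early stoppers already on another treatment at the visit (assumed).

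**4. Formula.** The share of late starters lost is h = D × f × L × w. The remaining late entrants show (D − h)/(1 − h). The pooled figure is s × (D − h)/(1 − h) + (1 − s) × D.

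**5. Results.**

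| f | w | h | Late entrants | Pooled | Shift (points) |
|---|---|---|---|---|---|
| 0.25 | 0.5 | 0.0125 | 0.1875/0.9875 = 19.0% | 19.5% | −0.5 |
| 0.40 | 0.5 | 0.020 | 0.180/0.980 = 18.4% | 19.2% | −0.8 |
| 0.25 | 1 | 0.025 | 0.175/0.975 = 17.9% | 19.0% | −1.0 |
| 0.40 | 1 | 0.040 | 0.160/0.960 = 16.7% | 18.3% | −1.7 |

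**6. Limits of the range.** If every patient is included at initiation (s = 0), the shift is zero. If every patient is included a full month after starting (s = 1, L = 1), the figure is 16.7% to 17.9% with w = 0.5 and 13.0% to 15.8% with w = 1.

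**7. Cross-check.** Let s instead be the share of all starters first met after starting, and e the share of their toxicity stops that occur, with a switch, before the visit. The reported figure is then (D − D·s·e)/(1 − D·s·e). With s = 0.5 and e = 0.10 this is 0.19/0.99 = 19.2%, inside the range in step 5, where e = f × L × w runs from 0.0625 to 0.20.

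The calculation ignores patients who stopped for other reasons and switched in the window. They would leave the denominator only, which offsets the shift slightly.

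**The case against.** **The criterion may be aimed elsewhere.** It may have been meant for concurrent CML therapy. That is plausible, but as worded it covers a patient who has switched.

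**Only a narrow group is lost.** A reader might infer that late entrants get in only if they are still tolerating bosutinib, so that the endpoint is too favourable by construction. The documents do not support that. Section 9.2.2 bars patients on another treatment. It does not bar those who have stopped without a successor or are in a temporary interruption. A calculation that removes every early toxicity stop overstates the loss unless all stoppers have switched, which is why w appears above.

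**The registry might still catch them.** A patient who starts bosutinib at a participating centre meets 9.2.1 at initiation. If not included then, the patient could be logged as eligible but not included, and the Annex 3.7 form offers an open reason field. This has some force. However, the Annex 3.7 instructions ask only for patients who satisfied the criteria and did not want to take part. Nothing directs a centre to log someone who fails a criterion when inclusion is considered.

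**Consecutive inclusion limits the problem.** Sections 9.5 and 9.9.2 ask for sequential inclusion of eligible patients, which should favour inclusion at initiation and keep s low. That reduces the size but does not remove the mechanism, because the request covers eligible patients only.

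**Analysis detail belongs in the SAP.** Section 9.7.2 defers detail to it. That is fair for the estimator, but not for the registry rule or the limitations text, which the protocol itself fixes.

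**Conclusion.** The point holds in a limited form. The entry window, the bar on other treatments, the registry restricted to eligible patients and the crude overall percentage together allow early related-AE stops followed by a switch to disappear unrecorded. The loss of these patients lowers the second primary endpoint, and the stated safeguards cannot detect it.

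The likely size is modest: about 0.5 to 1.7 points at a true 20%, well inside the 7.8-point sampling half-width, though systematic rather than random. It rests on assumed values for the share of late entrants, their lag, the timing of stops and the fraction switched, none of which the documents give. A reader might take the 13.0% to 15.8% case as the expected result. It requires every patient to be included a full month after starting and every stopper to have switched, whereas 9.2.1 also provides for starting at the end of the inclusion visit.

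**What to change.** **In 9.7.2:**
- Report related-AE discontinuation separately for patients included on or before first dose and for those included after it.
- Add a cumulative incidence of related-AE discontinuation measured from first dose, with delayed entry at the inclusion date.
- List separately any stops that occurred before inclusion in patients who were included, since they are not at risk at entry.

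**In the registry (9.4.1.7 and Annex 3.7):** for any remaining inclusion time, record patients who started and stopped bosutinib in the month before a possible inclusion visit, with the reason.

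**In 9.9.2:** state the residual selection and its direction.

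No eligibility or treatment rule needs to change.

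**Cost.** The initiation date is already collected (9.3), the inclusion visit supplies the entry date, and 9.7.3 already needs the discontinuation date for duration of treatment. The stratum included at initiation is smaller than the full cohort, so its interval is wider. Section 5 lists changes to data collection and to the analytical plan as examples of substantial amendments, so the change may need a formal amendment. The registry line also comes late: data collection began in October 2015 and 9.1 sets a four-year inclusion period, so inclusion would end around October 2019, about eight months after this version of February 2019. It would cover few patients, and most of the benefit lies in the stratified and delayed-entry reporting.
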